### 4. Study Procedures

Date: May 8, 2017

Principal Investigator: [name], MPH, NP

Application Number: IRB00081068

The proposed study is a single blinded, randomized controlled trial. The trial will evaluate a nurse case management intervention and determine differences in linking to HCV care (primary aim) and time to HCV treatment initiation (secondary aim) among persons co-infected with HIV. Patients with HIV and chronic HCV infection will be recruited from the Johns Hopkins University AIDS Service (JHUAS). After informed consent, participants will be randomized to a standard nurse case management protocol or enhanced usual outpatient care (100 per group), described below. Information flyers, provider referral, and targeted mailings will be used for recruitment.

## **Enrollment**

**Patient Population/Setting:** The Bartlett Specialty Practice (formerly the Moore Clinic for HIV Care) at the Johns Hopkins Hospital provides HIV primary care to approximately 3500 men and women over the age of 18 per year. The clinic serves a primarily adult, urban population, with approximately 80% of patients being African American. The average age of clinic patients is 49 years. Approximately 50% of patients with HIV are co-infected with HCV. In Maryland, HCV therapy currently must be managed by a hepatology, gastroenterology, or infectious disease specialist for Medicaid reimbursement. The Viral Hepatitis Specialty Clinic, staffed with hepatologists and hepatitis-focused infectious disease physicians and nurse practitioners, is located within the Bartlett Specialty Practice. As of May 2015, 480 HIV/HCV co-infected patients at the Moore Clinic had *never* attended an appointment at the Viral Hepatitis Clinic; 90 patients never went to their scheduled appointments and 390 patients had never been scheduled for HCV care. In addition, a number of patients have not attended an appointment at the Viral Hepatitis Clinic in the era of all-oral therapy (including the past year). The median time between referral and available new patient appointment at the Viral Hepatitis Clinic is one week.

**Recruitment:** Patients will either 1) self-refer by contacting the research team after seeing flyers posted in the Bartlett Specialty Practice waiting room or in an exam room research binder; 2) be referred from their HIV provider in clinic; 3) self-refer after receiving a targeted letter in the mail; or 4) self-refer after finding the study on clinicaltrials.gov, Trials @ Hopkins, or referral from the CFAR Hotline. Eligible prior study participants from the Principal Investigator's SUSTAIN study (NA\_00079147) who agreed to be contacted for future research (HIPAA form 3) will also be called. On a weekly basis, Bartlett Specialty Practice appointments will be reviewed electronically in EPIC to identify HIV/HCV co-infected patients scheduled for primary care visits. Letter notifications will be mailed to potentially eligible patients who have an upcoming appointment inviting them to contact the study team to participate in the research study. Daily, the primary HIV provider, registered nurse, or certified medical assistant will be approached to refer his or her eligible patients to the study. After the patient has contacted our research team to meet at the Bartlett Specialty Practice, a member of the study team will provide information regarding the study, answer any questions, and obtain informed consent. The PI will be available in person or via telephone to answer any questions when a student is present for the consent. Once enrolled, the study team will assign a study identification number (SIN) to the subject. This will be the primary mode of identification throughout the study. The SIN will appear on the consent form, the questionnaire, as well as all data collection forms. As part of the informed consent document, the participant will receive information on how to contact the investigators to discuss any of the nurse case management intervention components.

**Eligibility:** Adults who are co-infected with HIV and HCV who have not attended an HCV-specific appointment in the past year will be enrolled in the proposed study. Specific eligibility requirements are detailed in inclusion/exclusion criteria below.

Date: May 8, 2017

Principal Investigator: [name], MPH, NP

[figure not shown]
Application Number: IRB00081068

**Participant Consent:** Once the participant contacts the study team through a study flyer, letter, clinical trials database, or provider referral, the study will be explained with an emphasis on the use of random assignment to study groups. The consent process will be completed in a private area of the Bartlett Specialty Practice. To account for low levels of literacy, the study materials have been developed on a 5th grade reading level. Participants will also be given the option to have the consent form read aloud in its entirety. The consent form will be maintained in the study files and participants will be given the option of taking a copy of the signed consent form with them. They will be informed that retention of the form may lead to a breach of confidentiality if the information is shared with someone who does not already know their HIV and/or HCV status.

**Assessment of Protocol Comprehension Prior to Signing Consent:** After the consent form is read by the participant or aloud, the study team member will evaluate comprehension with three protocol-specific questions: 1) What are the problems we are trying to improve?; 2) How does this study plan to improve these problems?; 3) How will you be assigned to the different options in this study? We will deem the participant to have an acceptable level of comprehension based on his/her ability to answer those questions.

**Allocation:** This RCT will be conducted and reported following the CONSORT clinical trial guidelines. The study design is pictured in Figure 1. After recruitment and informed consent, patients will be randomized to the nurse case management intervention group or to the usual care group electronically. Participants will be randomized in a 1:1 fashion using REDCap, a secure online data collection program, to ensure balanced, random assignment to the intervention and usual care groups. REDCap employs a simple randomization technique. This strategy will ensure that the study team has no a priori knowledge of group assignment when enrolling and randomizing study participants.

**Blinding:** The study allocation will be single-blinded; no direct communication will occur between the nurse case manager and the HCV provider to avoid influencing the HCV management of the patient. The intervention will support the HIV provider and patient without influencing the HCV provider's decisions. The study team member completing data collection for the study outcomes will also be blinded to randomization to minimize bias in the results.

**Figure 1.** Integrated study flow and conceptual framework

\*HCV=hepatitis C virus; NCM=nurse case management; ART=HIV antiretroviral therapy

## Data Collection Measures:

The baseline characteristics questionnaire used in the proposed study has been thoroughly evaluated with over 1000 subjects (over 50% with HIV). The current study team has used this questionnaire with study participants in the Moore Clinic. Questions have been added or removed as applicable to this study and patient population. If a participant reports any alcohol use in the past 6 months on the questionnaire, the Alcohol Use Disorders Identification Test (AUDIT) will also be administered. The AUDIT consists of 10 items about recent alcohol use, alcohol dependence, symptoms, and alcohol-related problems. It was first developed in 1989 and has been validated in diverse international samples. The internal consistency reliability has been reported at 0.83 to the mid-0.90s. In a primary care setting, the AUDIT is intended to be administered by a nurse or social worker, and will be administered by a registered nurse in the proposed study. The research nurse case manager will counsel participants about alcohol use according to the recommended actions of the World Health Organization based on the individual AUDIT score. Participants scoring in Zone IV, suggesting alcohol dependence, will be referred to their Bartlett Specialty Practice social worker to discuss further counseling and treatment options.

The 19-item Brief Hepatitis C Knowledge Scale (Cronbach's  $\alpha=0.87$ ) will also be administered to measure baseline HCV knowledge. The Brief HCV Knowledge Scale includes a comprehensive list of items in its single factor that address the main aspects of HCV knowledge: prevention, risk reduction, transmission, and treatment. It was designed and tested on a diverse sample of patients, health care workers, and students with different socioeconomic and demographic backgrounds. It uses a simple true/false/don't know scoring system.

Depression can be associated with engagement in health services; therefore, the Patient Health Questionnaire (PHQ-9) will be administered. The PHQ-9 will be scored immediately. Participants scoring 10-19, indicating moderate depression, will be referred to their primary care provider for further follow up. Those

Date: May 8, 2017

Principal Investigator: [name], MPH, NP

Application Number: IRB00081068

with scores of 20 or greater (severe) will be referred to their primary provider, or, if the primary provider is not available, the covering urgent provider of the day, for further evaluation before the study is continued.

All questions in the protocol will be asked in a private area and can be administered by a study team member in 30-45 minutes. In addition to the subject questionnaire, each instrument contains a section for the research team to interrogate the patient's medical record to verify specific pieces of the medical history. These variables of interest include:

- CD4+ T cell count
- HIV viral load
- Prescribed HIV treatment
- Year of HCV diagnosis
- HCV RNA
- Fibrosis score
- HCV genotype
- HCV referral history
- HCV appointment history
- HCV treatment initiation barriers
- Hopkins appointment no-show rate

In addition to baseline and outcome data collection, monthly activity logs will be collected for each study participant, independent of allocated study arm. The type, quantity, and content of all encounters with a study participant in the Johns Hopkins system will be recorded each month, including nurse visits. This will define usual care for Bartlett Specialty Practice patients. The type, quantity, and content of all Care2Cure study visits will also be recorded to define the dose of the intervention. Data will be collected from the study participant's Epic record and the interventionist's notes.

**Enhanced Usual Care:** After randomization into the enhanced usual care arm, the nurse case manager will provide participants with the CDC HCV Fact Sheet and phone number for the CFAR Research Study Hotline. Participants will then be referred to the usual clinic appointment check-out process. To check-out of Bartlett Specialty Practice appointments, participants return to the front desk with a paper billing page and printed appointment referrals if applicable. The administrative staff closes the appointment encounter and gives the patient the phone number for the Johns Hopkins Hospital central scheduling phone line to schedule referral-based appointments. Patients are responsible for calling central scheduling to set up the specialty appointment. If an appointment is scheduled, all patients receive an automated appointment reminder call 2 days before the scheduled appointment from Johns Hopkins Hospital. Patients at the Bartlett Specialty Practice have access to nurse case managers and social workers assigned by their primary providers. Participants in the enhanced usual care arm will continue to have usual access to these services. Per the Bartlett Specialty Practice standard care protocol, once a prescription is written for HCV treatment, the assigned nurse case manager will work with the patient to coordinate HCV care; however, HIV nurse case managers are not directly involved in HCV care until after prescription for HCV treatment is written, which is the gap the proposed study seeks to fill.

### **Nurse Case Management Intervention Phase 1 – Linking to Care:**

Following informed consent, randomization, and completion of the baseline questionnaire, participants allocated to the intervention group will receive the first phase of the nurse case management (NCM) intervention (Table 1). This phase of the intervention will increase linkage to HCV care through NCM consisting of nurse-initiated referral, strengths-based HCV education, patient navigation, and HCV appointment reminders. The research nurse case manager will initiate an HCV referral for participants randomized to the

Date: May 8, 2017

Principal Investigator: [name], MPH, NP

Application Number: IRB00081068

intervention group via the electronic health record. This will send a cue to the HIV provider to approve the referral and minimize the barrier of non-referral by the provider. Participants will then receive brief strengths-based HCV education. Strengths-based education can improve knowledge and motivation to achieve health-related goals in PLWH. The research nurse case manager will help participants identify their strengths within the context of engaging in HCV care, including social support and engagement in HIV primary care. HCV education will include transmission, symptoms, treatment, and risk reduction. Participants will also identify barriers to linkage to care and form a plan with the research nurse case manager to minimize these barriers; this may include referrals to benefits counseling, substance use, mental health services, and the Johns Hopkins “Cure Club” HCV support group.

Linkage to care will be defined as attendance at one or more appointment within the HCV treatment pathway via the Viral Hepatitis Center, including either traditional clinical care at the Bartlett Specialty Practice or an HCV treatment-providing clinical trial within the Viral Hepatitis Center. This will ensure that participants enrolled in the Care2Cure study have the opportunity to engage in HCV treatment in all pathways offered by the Viral Hepatitis Center and inherent in Johns Hopkins Hospital’s standard of care as an academic institution and research center. Independent of randomization allocation, all study participants will be asked in the baseline characteristic questionnaire if he/she would like to be referred to a clinical trial, with the option to refuse or opt out of trials for non-FDA approved treatments. Based on this participant preference, eligibility for actively recruiting clinical trials at the Viral Hepatitis Center will be assessed. Participants will then be referred by the study nurse case manager to either traditional care at the Bartlett Specialty Practice, a clinical trial with no investigational drug, or a clinical trial with an investigational drug, as eligible and available.

Multiple strengths support this approach to the outcome of linkage to care. In Maryland, patients must have a Metavir score greater than or equal to 2 to receive HCV treatment (Maryland Department of Health and Mental Hygiene, 2015). Linking patients to clinical trials that offer treatment to patients in all stages of liver disease, including F0 and F1, removes this barrier to treatment. This approach also minimizes selection bias. Participants who choose to receive HCV treatment through a trial may be different than those who seek care through the traditional clinical pathway; the Care2Cure study will include both.

Because appointment scheduling is a known barrier to linkage to care, patient navigation will include either a) calling central scheduling during the visit so the research nurse case manager can navigate participants through the Viral Hepatitis Clinic scheduling process or b) calling a clinical trial recruitment number to link eligible participants with an HCV-treating clinical trial. Participants also will be encouraged to call the Care2Cure research nurse case manager for needs relating to linking to HCV care throughout the study period. All contacts and amount of time spent with the study participants will be recorded by the research nurse. Participants will receive a personalized HCV appointment reminder in addition to the automated phone reminder all patients receive through the Johns Hopkins Hospital usual care system. A plan for contacting participants for personalized appointment reminder will be made, including the best mode of contact (phone, text, or email) and time of day. Participants will be contacted 1 day before their scheduled Viral Hepatitis Center appointment (either at the Bartlett Specialty Practice or a clinical trial) for an appointment reminder in addition to the automated JHH reminder 2 days before the appointment. If the scheduled Viral Hepatitis Center appointment is greater or equal to 2 weeks (10 business days) from the date of the baseline visit, participants will also be contacted one week before the appointment for a reminder.

The medical record will be reviewed 60 days after the baseline visit to verify whether the participant was registered for one or more Viral Hepatitis Clinic appointment since randomization if referred to the Bartlett Specialty Practice HCV provider. If the participant was referred to a clinical trial, attendance at a study appointment will be confirmed with that study coordinator.

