## **Nurse Case Management Intervention Phase 2 – Treatment Initiation:**

Date: May 8, 2017

Principal Investigator: [name], MPH, NP

Application Number: IRB00081068

This phase of the intervention will decrease time to HCV treatment initiation by using a nurse case manager to coordinate communication about antiretroviral therapy (ART) modifications between the patient, HCV provider documentation, and HIV provider. Participants who are enrolled in another clinical trial will not be included in this phase. Participants in clinical trials that provide medication (such as the CHAMPS study or an investigational drug trial) will receive an intervention to initiate HCV treatment within that trial. These participants are expected to follow a different timeline than clinical patients and face different challenges. Therefore, this phase will include a subgroup of consented Care2Cure study participants who link to an appointment at the Bartlett Specialty Practice HCV provider.

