## 7. Study Statistics

### Analysis:

Data will be cleaned and efforts made to minimize the effects of missing data. All provider visits at Johns Hopkins are registered in the electronic medical record, so absence of a registered appointment during the study period will be considered non-attendance for the primary outcome variable. A computer-based data collection method will be used for data collection of independent variables in attempt to minimize missing data. Exploratory and descriptive analysis will be completed for all study variables. Variables will be tested for normality and examined with means and standard deviations or medians and interquartile ranges accordingly. Baseline characteristics comparing the two groups (usual care vs. intervention) will be assessed. Any differences between the groups will be adjusted for in further analysis. The significance level will be set at 0.05. All tests will be two-tailed and analyzed by intention-to-treat.

**Primary Outcome:** The primary outcome is linkage to care, measured by attendance at the Viral Hepatitis Center (either traditional care or an HCV-treating clinical trial) within 60 days of randomization (yes/no). This hypothesis will be tested using a two-sample z-test for the difference in independent proportions comparing the intervention to usual care groups.

**Secondary Outcome:** The secondary outcome is time to HCV treatment initiation, measured by the number of days from randomization to the date HCV treatment is initiated according to the medical record. Kaplan Meier estimates will be conducted to compare time to HCV treatment initiation between participants in the intervention group and the usual care group, and a log-rank test will be used to test the difference. Covariates (age, sex, race/ethnicity, HCV knowledge, substance use, fibrosis score, CD4+ T cell count, HIV viral load, care giving responsibilities, and participation in Cure Club) will be included in the Cox regression model. To account for a time to treatment initiation greater than the observed time period of 6 months, right censoring will be implemented for participants who have not initiated HCV treatment at the end of the 6-month period.

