### **Sample Size Justification:**

Currently, 40% of new Viral Hepatitis Clinic appointments are attended by patients. Based on prior studies testing the intervention components in similar populations, including persons living with HIV and/or substance use disorders, it is expected that the intervention will improve the primary outcome of linkage to care by 18-30%. Although the effect size is not known in the context of HCV, we estimate an improvement in linkage of 20% (i.e., 60% attendance [0.60] in the NCM group compared to 40% attendance [0.40] in the usual care group) based on these prior studies. Using these figures and a two-tailed test with an alpha of 0.05, a conservative estimate of the total sample size required to achieve 80% power is 97 per group, or a total of 194 participants (G\*Power 3.1.9.2). With a sample size of 100 participants in each group, there should be an adequate number of participants to detect a difference in proportion of linkage to care for the primary aim.

For Phase 2, participants with successful linkage to clinical care from Phase 1 (those who attend  $\geq 1$  appointment at the Viral Hepatitis Clinic within 60 days) will be included. Therefore, the eligible sample size will be less than 40-60% of the original sample size because a linkage to care proportion of 0.40-0.60 is expected, and some participants will link to a clinical trial and not be included in this outcome. This is a secondary outcome and estimated effect size is unknown. However, with 100 participants in this group (half of the total sample size), we will have 90% power to detect a hazard ratio of 2.

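### Aim 2's unstratified log-rank test pools F0–F1 clinic participants, who on the protocol's own account have little chance of starting treatment, with those who can start; it loses power and shows a diluted effect

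*Combined protocol and SAP*

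**What the plan says.** All references are to the combined protocol and SAP.

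- **Access to treatment (Section 4, Phase 1 – Linking to Care).** "In Maryland, patients must have a Metavir score greater than or equal to 2 to receive HCV treatment". The same paragraph presents trials that accept all liver disease stages, F0 and F1 included, as the way past this barrier.
- **Who is in Phase 2 (Section 4, Phase 2 – Treatment Initiation).** "Participants who are enrolled in another clinical trial will not be included in this phase". The phase is for those who link to the clinic's HCV provider. Sample Size Justification adds that trial-linked participants do not count in this outcome.
- **Eligibility (Section 5).** Chronic HCV is required. No fibrosis criterion appears among the inclusion or exclusion criteria.
- **Allocation (Section 4, Allocation).** "Participants will be randomized in a 1:1 fashion using REDCap", and "REDCap employs a simple randomization technique". Fibrosis is not a randomization stratum.
- **Aim 2 analysis (Section 7, Secondary Outcome).** Days from randomization to treatment start, summarized by Kaplan-Meier; "a log-rank test will be used to test the difference". No stratum is named. Non-starters are censored at 6 months. Fibrosis score is one of ten covariates listed for a Cox model.
- **General rules (Section 7, Analysis).** "The significance level will be set at 0.05". "All tests will be two-tailed and analyzed by intention-to-treat".
- **Power (Section 7, Sample Size Justification).** "with 100 participants in this group (half of the total sample size), we will have 90% power to detect a hazard ratio of 2". No event count, initiation rate or fibrosis mix accompanies this.
- **Data (Section 4, Data Collection Measures).** Fibrosis score is among the items taken from the medical record.

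**The concern.** Taken together, these sections remove from the Aim 2 set the route that opens treatment to F0–F1, but keep F0–F1 participants who attend the clinic. Those people sit in the risk set for the full 6 months in both arms with little chance of an event.

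This does two things to an unstratified comparison. It lowers the number of events for a given sample size. It also dilutes the contrast: participants who can start leave the risk set as they start, faster in the better arm, so the remaining risk set fills with people who will not start and the hazards in the two arms converge. A real Phase 2 effect would look smaller on the curves and be more easily missed by the named test, although the variable that explains the dilution is already collected.

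**Working it through.** **1. The plan's own figure.** Inputs: two-sided alpha 0.05, 90% power, hazard ratio 2, 1:1 (Section 7; Allocation).

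- Schoenfeld: 4 × (1.960 + 1.282)² / (ln 2)² = 87.5, so 88 events.
- Freedman: (1.960 + 1.282)² × (3/1)² = 94.6, so 95 events.

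If all 100 participants are events, power is 91.5% (Freedman) or 93.4% (Schoenfeld). The stated 90% is therefore reproduced only if roughly 88 to 100 of the 100 start treatment within 6 months.

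**2. Cap on events.** If F0–F1 participants do not start, starts cannot exceed 100 × (1 − F0–F1 share). At shares of 20%, 40% and 60% the cap is 80, 60 and 40. Schoenfeld power at those maxima is 87.3%, 76.6% and 59.2%, before any dilution. Stratifying does not recover these events.

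**3. Why the effect is diluted.** Let π be the F≥2 share and λ the starting hazard in an arm's F≥2 participants. The arm's pooled hazard at time t is λ × πS(t) / (πS(t) + 1 − π), where S(t) is the F≥2 proportion not yet started. Take π = 0.6, 50% of control F≥2 starting by 6 months and hazard ratio 2, so that intervention S = 0.5² = 0.25:

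- At randomization the pooled hazard ratio is 2.
- At 6 months, control: λ × 0.30 / 0.70 = 0.429λ. Intervention: 2λ × 0.15 / 0.55 = 0.545λ. Ratio 0.545 / 0.429 = 1.27.

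Averaged over the window, the unstratified hazard ratio is about 1.70.

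**4. Power by simulation.** Assumptions, because the documents supply none: 50 per arm, exponential times, hazard ratio 2 in F≥2, no F0–F1 starts, all scores recorded, censoring at 6 months, 4,000 runs (simulation error at most about 0.8 points per figure).

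| Control F≥2 starting | F0–F1 share | Unstratified power | Stratified power | Unstratified HR |
|---|---|---|---|---|
| 50% | 20% | 56% | 68% | 1.83 |
| 50% | 40% | 36% | 54% | 1.70 |
| 50% | 60% | 22% | 40% | 1.61 |
| 70% | 20% | 55% | 79% | 1.70 |
| 70% | 40% | 31% | 67% | 1.52 |
| 70% | 60% | 16% | 49% | 1.41 |

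Repeat runs of the second row give about 37% and 55%, the figures quoted in this point. Stratified, the hazard ratio stays at 2.03 to 2.08. With no F0–F1 events the stratified test equals the test within F≥2, which gives an analytic check on the second row: events = 0.6 × (50 × 0.50 + 50 × 0.75) = 37.5, and Schoenfeld power is 56.4%.

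**5. Where the gain shrinks.**

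- At 30% control initiation it is about 5 to 7 points.
- With all 200 analysed, 60% F≥2, 50% control initiation in F≥2 and the same hazard ratio in F0–F1, it is about 10 points if 10% of control F0–F1 start and about 4 points if 20% do (88% against 92%).
- In the setting of the second row, stratified power falls to about 52%, 46% and 39% when 20%, 50% and 80% of scores are unrecorded. The unstratified test stays at about 36–37%, so the gain at 80% unrecorded is about 2 points.

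**The case against.** **The Cox model already adjusts for fibrosis.** This is the strongest objection, and most of it stands for the estimate. Under the assumptions of step 4 with 50% control initiation, entering fibrosis as a plain 0–4 score with no other covariates gives a median treatment hazard ratio of 1.95, 1.98 and 1.91 at 80%, 60% and 40% F≥2. Power is 61%, 51% and 37%, against 66%, 58% and 42% stratified in the same 400 runs. A reader might infer that the trial's hazard ratio would reflect the fibrosis mix rather than the intervention; the adjusted model in the plan does not support that. The named hypothesis test and the curves remain unadjusted.

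**The analysis set is unsettled.** Section 2 frames Aim 2 by randomized arm and Section 7 says intention-to-treat, whereas Sample Size Justification counts only clinic-linked participants. Phase 2's exclusion says who receives that phase, not expressly who is analysed. If all 200 are analysed, F0–F1 participants who start through a trial may count and the loss is smaller (step 5). This stands, and it is why the sections need reconciling.

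**The access rule may not be absolute.** A reader might infer that F0–F1 participants cannot start in the clinic at all. The text is one general sentence attributed to a 2015 state document, in a protocol dated May 2017. It does not say which payers are bound, whether exceptions exist, or whether it held throughout enrolment. Little chance of starting is as far as it goes.

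**Scores may be missing.** Participants had no viral hepatitis visit in the past year, and many clinic patients had never been scheduled for HCV care. The gain shrinks accordingly, but the stratified test was not worse in any setting run.

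**Conclusion.** The point holds as a loss of power and a diluted effect in the named Aim 2 test, a secondary outcome. At 60% F≥2 and 50% control initiation the cost is about 18 points of power (37% against 55%). It is larger at 70% initiation and falls to a few points under the conditions in step 5. Every figure rests on assumed fibrosis shares and initiation rates, and on F0–F1 participants rarely starting in the clinic.

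Two stronger readings are not supported. One is that F≥2 should become the Aim 2 population: Section 2 sets the aim for persons with HIV/HCV co-infection, and the remedy does not require narrowing it. The other is that the test is shown to be biased. If F0–F1 shares differed by arm in a set formed after randomization, the unstratified test could reject too often (17–28% with no effect and shares of 40% control against 20% intervention). However, the documents give no shares by arm, so this is a possibility and not a finding.

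**What to change.** In Section 7, Secondary Outcome:

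1. Make the Aim 2 test a log-rank test stratified by baseline fibrosis (F0–F1, F≥2, not recorded).
2. Stratify the Cox baseline hazard by the same three groups, in place of a fibrosis covariate of unstated coding.
3. Show Kaplan-Meier curves by stratum as supportive displays. Keep Aim 2 for everyone in its analysis set.
4. Reconcile Section 2, Phase 2, Section 7 Analysis and Sample Size Justification on whether that set is all randomized or clinic-linked participants, and on how trial-linked participants are handled.

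Items 1 to 3 are wording changes that need no new data or visits, because the score is already abstracted. The cost is small: participants with no recorded score form a third stratum that reduces the gain, and lost events are not restored.
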